10.3. The Number of Participants

This will be a feasibility study and as such an underpowered study with no power calculations. It is expected that if the results are favourable then a full multi-centred clinical trial will follow.

As such, a sample size of 50 participants per site (JCUH and NSECH) as well as 100 (NEAS) clinicians will be expected over the 6 month study period (N=200). It is unknown how many participants will drop out of the study, however, due to a single study visit it is believed that there will be a very low drop/withdraw rate.

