1. SYNOPSIS

Study Title	Spinal Motion Restriction Feasibility (SMRF) Study. A prospective randomised two centre comparative study to determine if there is a difference in clinical outcomes and patient experience comparing Spinal Motion Restriction techniques which include the traditional use of a rigid cervical spine collar versus the omission of a rigid collar.			
Internal ref. no. / short title	Spinal Motion Restriction Feasibility (SN	IRF) Study.		
Protocol Version	V1.1			
Protocol Date	24/01/2020			
Study Design	A prospective randomised two centre co	omparative intervention study.		
Study Participants	Patients who have experienced a mechanism of injury that would suggest a potential SCI.			
Planned Sample Size	50 intervention participants, 50 control	participants and 100 clinicians		
Planned Study Period	16 months in total (6 months intervention/control followed by 6 months control/intervention at each of two sites. 1 month training for clinicians and research assistants with 3 months data collation, analysis and writing up of conclusions/discussion).			
Number of Study Sites	Three. North East Ambulance service Northumbria Specialist Emergency Care			
	Objectives	Outcome Measures		
Participant Clinical Outcomes	To compare the clinical outcomes of Spinal Motion Restriction principles where intervention group omit the use of rigid collar on potential SCI versus current standard immobilisation practices which includes the use of rigid collar.	 Time: on scene, to scan, in ED. Neurology (Gross) Fractures/Injury Tissue Viability/Pressure sores Compliance 		
Participant Experience	To compare the patient experience outcomes of Spinal Motion Restriction principles where intervention group omit the use of rigid collar on potential SCI versus current standard immobilisation practices which • Comfort • Pain • Understanding • Complications (anxiety, breathing)			

	includes the use of rigid collar.	
Clinician Experience	To compare the clinicians experience of Spinal Motion Restriction principles where intervention group omit the use of rigid collar on potential SCI versus current standard immobilisation practices which includes the use of rigid collar.	Clinician experience (Qualitative)

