3. BACKGROUND AND RATIONALE

Within the United Kingdom (UK), Cervical Spinal Cord Injury (SCI) is a rare event. Traditional three-point immobilisation for spinal stabilisation has been the standard clinical practice for trauma patients with suspected cervical SCI for over 50 years.

The literature highlights a variable global incidence of traumatic SCI of between 9.2 and 246 per million persons per year with a prevalence of 236 to 1,298 per million population (Furlan et al., 2013). In their pre-hospital study Oteir et al. (2016) estimated that of the 106,059 patients who were identified as having potential traumatic SCI, less than 0.5% had confirmed SCI.

Contemporary literature and consensus reports are now challenging traditional practices in favour of a pragmatic second generation of supportive techniques that follow patient centred Spinal Motion Restriction principles. Spinal Motion Restriction principles include moving away from the routine application of rigid collars and back boards, encouraging self-extrication when appropriate, manual in line stabilisation and alternative approaches to Spinal Motion Restriction while improving patient comfort. These principles empower clinicians to tailor their approach to Spinal Motion Restriction and ensure effective and safe patient centred care.

Initial recognition of the need for immobilisation was documented by Rogers (1957) who analysed a case series involving 77 patients who all had significant spinal injuries. Of these 77 cases it was noted that 8 patients developed new or worsening symptoms after arrival at the hospital. Upon reflection, it was hypothesised that if these patients had an adjustable neck brace fitted for the purposes of extrication and transfer then some of these deteriorations may have been avoided.

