Based upon the limited literature the aim of this study is to determine if there is a difference in clinical outcomes and patient experience, as well as the experiences of the clinicians taking part in the study, comparing traditional immobilisation techniques, which include a rigid collar versus Spinal Motion Restriction (SMR) techniques which include the omission of a rigid cervical spine collar.

Brief description of the intervention:

Patients experiencing a mechanism of injury that would suggest a potential spinal injury will have the JRCALC immobilisation guidelines (Canadian C spine rules) applied on assessment. If, after assessment, the patient is positive for spinal stabilisation then the intervention group will apply Spinal Motion

Restriction (SMR) principles which omit the use of a rigid collar. The patient will be manged as standard with the only change being the omission of the rigid collar. To assist is providing a visual marker for the patients ongoing management an additional sticker will be placed upon the head blocks/tape/blanket rolls which states 'C-Spine NOT Cleared'. Participants from both the control and intervention groups as well as the clinicians themselves will be asked to complete an experience questionnaire after the event.

Risks and benefits: There is little evidence for or against rigid collar use. There is a potential that if patients are managed poorly (rough handling) then neurology may be compromised. The benefits are that on scene times may be reduced (patient comfort through environmental factors) and overall patient comfort will be improved and reducing the risk of pressure sores and associated risk of infection.

The study is applicable to any patient experiencing a significant mechanism of injury that would suggest a spinal cord injury such as (but exclusive to) fall from height, Road Traffic Collision, assaults etc. It is believed the results of the study will be generalised and applicable to the wider trauma population with potential spinal cord injury. It in no way underplays the seriousness or risks associated with a spinal cord injury.

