10.2. Interim analysis

The Data Monitoring Committee will monitor the accumulating outcome data, and one of their roles is to recommend cessation of recruitment if a clear result has been reached (i.e. if either intervention or control is clearly superior). We suggest that different thresholds of evidence for early termination are adopted if non-collar or collar being more effective, as it is likely that stronger evidence would be needed to change current practice (collar use) if non-collar use is found to be superior. We therefore propose that interim analyses are conducted frequently in the early stages of the trial, so that, if collar use is superior, this can be detected early. Thus we will minimise any risks to patients while producing robust evidence that will change practice.

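### Section 10.3 ties the full trial to undefined favourable results from a study it calls underpowered, while section 10.2 promises practice-changing evidence that 50 v 50 patients cannot supply

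*Protocol*

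**What the plan says.** Protocol section 10.3 states: "This will be a feasibility study and as such an underpowered study with no power calculations". The next sentence is the only statement on progression: "It is expected that if the results are favourable then a full multi-centred clinical trial will follow". No section defines favourable.

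Section 10.2, on interim analysis, closes with: "Thus we will minimise any risks to patients while producing robust evidence that will change practice".

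The purpose is comparative throughout. Section 3 says that "the aim of this study is to determine if there is a difference in clinical outcomes and patient experience", with clinicians' experience added. All three objectives in the synopsis and in section 4 are comparisons of the two methods. Sections 10.1 and 10.4 make estimation of treatment effects, with 95% confidence intervals, the focus of the analysis and assign logistic regression to dichotomous outcomes.

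The planned size is given in the synopsis as "50 intervention participants, 50 control" participants. Section 3 supplies the only relevant event rate: of patients with potential traumatic SCI in a cited pre-hospital cohort, "less than 0.5% had confirmed SCI".

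**The concern.** A feasibility study normally asks whether the full trial can be run. Here no objective concerns recruitment, consent after the event, or completeness of follow-up. Compliance is listed as an outcome, but it is not linked to progression. The only condition attached to the next trial is that results be favourable, and the only results the objectives define are comparisons between arms.

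Two things are at stake. First, the sponsor could pursue or drop a full trial on an outcome difference that this sample cannot establish, while the quantities that decide whether such a trial is workable have no stated role. Secondly, sections 10.2 and 10.3 make incompatible claims about the strength of the evidence, and a reader of the final report could rely on the stronger one. Rare neurological harm is the most sensitive case, since a study of this size will probably see few or no events.

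**Working it through.** **The plan's own figure.** 50 + 50 patients + 100 clinicians = 200, as section 10.3 states. There is no power calculation to reproduce.

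**Inputs.** 50 patients per arm (synopsis). Confirmed SCI below 0.5% (section 3), with 0.5% used as the upper value. Two hospitals crossed over after six months (sections 5 and 7.4), hence four site-periods of about 25 patients if recruitment is even. Assumed, because the protocol gives none: effect sizes of 0.2 to 0.8 SD, two-sided 5% (implied by the 95% intervals), within-period intracluster correlation (ICC) 0.01 to 0.05, and cluster autocorrelation (CAC) 0.5 to 0.8.

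**1. Precision of a standardised difference, ignoring clustering.**
- SE = sqrt(2/50) = 0.20 SD; 95% half-width = 1.96 × 0.20 = 0.39 SD.
- Wrong sign when the true benefit is 0.2 SD: Φ(−0.2/0.20) = Φ(−1) = 16%. With no true effect it is 50%.
- Power = Φ(d/0.20 − 1.96):

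| True difference (SD) | 0.2 | 0.3 | 0.5 | 0.8 |
|---|---|---|---|---|
| Power | 17% | 32% | 70% | 98% |

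**2. Clustering.** Design effect = 1 + (m−1)·ICC − m·ICC·CAC, with m = 25.
- ICC 0.01, CAC 0.8: 1 + 0.24 − 0.20 = 1.04.
- ICC 0.05, CAC 0.5: 1 + 1.20 − 0.625 = 1.575.
- At 1.575 the SE is 0.20 × sqrt(1.575) = 0.25 SD, the half-width is 0.49 SD, and the wrong-sign chance at 0.2 SD is Φ(−0.2/0.251) = 21%. Power at 0.5 SD falls to 51% (69% at 1.04).

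**3. Rare neurological harm, with confirmed SCI as proxy.**
- Expected cases in 100 patients: at most 100 × 0.005 = 0.5.
- P(none in 100): at least 0.995^100 = 0.61.
- Exact two-sided 95% upper limit for 0 of 50: 1 − 0.025^(1/50) = 7.1%, which is 14 times the 0.5% rate.
- A finite unadjusted odds ratio needs at least one event in each arm: (1 − 0.995^50)² = (1 − 0.778)² = 4.9% at most.

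**4. What the sample can do for feasibility.** For an illustrative proportion of 80%:
- Ignoring clustering: per arm 1.96 × sqrt(0.8 × 0.2/50) = ±11 points; overall 1.96 × sqrt(0.8 × 0.2/100) = ±8 points.
- With ICC 0.05 and CAC 0.5, the correlations add instead of cancelling. Per arm (two site-periods at different sites) the design effect is 1 + 24 × 0.05 = 2.2, giving ±16 points. Overall it is 1 + 1.2 + 0.625 = 2.825, giving ±13 points.

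Feasibility proportions are therefore estimable, but less tightly than the unclustered figures suggest.

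**The case against.** The best case for the protocol has five parts.

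- *The sentence in 10.3 is an expectation, not a decision rule.* True: it does not say that a trial would be abandoned otherwise, and it does not mention outcome differences. A reader might infer a formal go/no-go rule, and the text does not support that. What stands is that it is the only progression statement, and the objectives leave nothing but comparisons for it to refer to.
- *The analysis focuses on estimation with confidence intervals.* This is sound and should be kept. It does not fit with a promise of practice-changing evidence.
- *Feasibility data are collected.* Also true. Compliance is an outcome (section 4) and is audited (13.1), near-complete capture of eligible patients is an aim (7.5.1), missed patients are audited (13.2), and recruitment by arm is monitored (7.5.2, 13.3). The gap is narrower: none of this is linked to progression.
- *Sparse-event handling belongs in the SAP.* Largely fair, since 10.1 defers detail to it. In addition, confirmed SCI in an external cohort is not the same as the gross neurology recorded here, and no rate is given for fracture or pressure damage. A reader might infer that logistic regression fails for every dichotomous outcome, but the documents do not show that.
- *Nothing says that zero events would be read as safety.* Correct, and section 9 requires a halt and investigation if new neurology develops after transfer. The caution concerns interpretation of a likely result.

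**Conclusion.** The point holds in limited form. Progression is tied to an undefined favourable result that 50 v 50 patients cannot reliably establish for modest effects or for rare neurological harm, and 10.2 contradicts 10.3 on the strength of the evidence. The contradiction and the missing criteria rest on the text alone, apart from the well-supported inference about what favourable refers to.

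The size depends on assumptions. The half-width of 0.39 SD and the 16% wrong-sign chance ignore clustering and take 0.2 SD as an assumed effect. The figures of 0.5 cases, 61% and 7.1% use confirmed SCI as a proxy and assume the cited cohort's rate carries over. Excluding patients with obvious new neurology (6.3) would lower the rate, while a broader definition of neurology would raise it.

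A reader might go further and infer that the decision would rest mostly on chance. The documents do not support this: for a large difference in comfort or pain, power is 70% at 0.5 SD and 98% at 0.8 SD before clustering, and at 0.5 SD the direction is right 99% of the time. With no effect size in the protocol, the share due to chance cannot be fixed.

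**What to change.** 1. **Section 10.3.** Replace the progression sentence with pre-specified feasibility criteria based on data already planned: recruitment by site-period, consent after the event among eligible patients, use of the allocated method in each arm, and completeness of the questionnaire and the 5-day clinical data. The sponsor sets the cut-offs. State the precision of each proportion allowing for site-period clustering. The consent rate needs all eligible patients as its denominator, because section 7.3 admits no information without signed consent and the other measures would otherwise describe consenters only.
2. **Sections 3, 4 and 10.2.** Add these quantities to the aim and objectives, delete the claim of practice-changing evidence, and describe outcome comparisons as exploratory estimates with confidence intervals.
3. **Sections 10.1 and 10.4.** Report neurology, and any other dichotomous outcome with too few events or an empty cell, as counts by arm with exact intervals instead of logistic regression. State that these intervals ignore clustering and that zero events is not evidence of safety.

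**Cost.** No new patients or procedures. The study gives up a confirmatory claim it cannot support. Restating the aim is more than editing, and may need Steering Committee agreement (12.6) and, if substantial, REC/HRA approval (14.3).

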5. STUDY DESIGN

Participants will be pre-randomised based on the hospital sites they are attending. Northumbria Specialist Emergency Care Hospital (NSECH) and James Cook University Hospital (JCUH) are the two nominated research sites. Initially the two participating sites will be randomised to either intervention or control site. After six months duration the sites will reverse and whichever site was originally randomised as intervention site will become the control site for the remaining six months and the control site will become the intervention site.

The participants will be selected by the attending trained North East Ambulance Service (NEAS) personnel and enrolled into the study if they are positive for a mechanism of injury and clinical assessment that would suggest a Spinal Cord Injury. NEAS are acting as the Participant Identification Centre (PIC) for patient participants and research site for clinical experience.

Control group: Over a six-month period this group will be managed in the traditional manner. This will involve patients being advised of the need for a hard collar, blocks and tape. For a variety of reasons this may not be tolerated by some patients and this non-compliance will be recorded for the purposes of the study outcome results, although these patients will be included in the 'traditional' method of motion restriction numbers.

Intervention group: Over a six-month period intervention group patients transported by NEAS crews with a suspected cervical spine injury being taken to the randomised intervention site with their cervical spine motion restriction managed in accordance with the proposed flow chart (appendix B). For these patients unless the exclusion criteria apply, no hard collars will be employed.

After the initial six-month intervention/control phase the receiving sites will reverse the process and undertake another six month phase as the control/intervention phase.

Each participant enrolled will be followed up on site by a research clinician and clinical outcomes measured as stated on the Computerised Tomography (CT) report and/or patient notes. Patient experience outcomes will be collected by a research clinician using a dementia friendly adapted Likert scale type survey prior to discharge or at 72 hours whichever is earliest. Participants will also be

CONFIDENTIAL: Spinal Motion Restriction Feasibility Study (SMRFS).

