7.8. Definition of End of Study

The end of study is the date of the last visit / telephone follow up / home visit of the last participant which is expected to be on or around 30th November 2019.

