9.2. Reporting Procedures for Serious Adverse Events

A serious adverse event (SAE) occurring to a participant should be reported to the REC that gave a favourable opinion of the study where in the opinion of the Chief Investigator the event was 'related' (resulted from administration of any of the research procedures) and 'unexpected' in relation to those procedures. Reports of related and unexpected SAEs should be submitted within 15 working days of the Chief Investigator becoming aware of the event, using the HRA report of serious adverse event form (see HRA website).

All of the patients in this study will have experienced an acute injury requiring an emergency ambulance for transportation to either a trauma unit or major trauma centre and as such will be expected to have

CONFIDENTIAL: Spinal Motion Restriction Feasibility Study (SMRFS).

injuries from the initial insult of the trauma. Through monitoring of the receiving sites, it is believed that if there is an obvious deterioration/change between pre and post management of the intervention group compared to the control group then the incident must be reported and study halted.

All serious adverse events should be reported to the site primary investigator and chief investigator using the appropriate form at the earliest opportunity. (See appendix F)

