9.3. End of the Study

The study will end when the final patient has been recruited and their outcomes extrapolated from the patient notes or classified as lost to follow up. This is believed to be approximately 7 months from the start of participant recruitment.

The study will be stopped prematurely if:

- Mandated by the ethics committee,
- There is an obvious differentiation between the outcomes of control and intervention groups,
- There is a serious adverse event which prevents the ongoing study to be viable.

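### Sections 10.3, 9.3 and 7.8 give durations and an end date that do not fit the 12-month crossover; following 10.3 or 9.3 would lose most or all of period 2 and leave largely a comparison of hospitals

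*Protocol*

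**What the plan says.** Three parts of the protocol agree on a two-period design. The synopsis plans "6 months intervention/control followed by 6 months control/intervention at each of two sites", inside a 16-month study. Section 5 says: "After six months duration the sites will reverse". Section 7.4 randomises the two hospitals to opposite orders of six months intervention and six months control.

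Three other parts do not fit it:

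- Section 10.3 plans "a sample size of 50 participants per site (JCUH and NSECH) as well as 100 (NEAS) clinicians", and says that these "will be expected over the 6 month study period (N=200").
- Section 9.3 ends the study once the last patient has been recruited and their outcomes obtained, and adds: "This is believed to be approximately 7 months from the start of participant recruitment".
- Section 7.8 ends the study at the last follow-up of the last participant, "which is expected to be on or around 30th November 2019". The synopsis dates the protocol 24/01/2020.

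The patient totals are given by arm in the synopsis ("50 intervention participants, 50 control") and by site in sections 4 and 10.3 (50 at each hospital). No section gives a number per site per period, and none reconciles the durations.

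**The concern.** Allocation is by hospital and changes only at month 6. Before then, every intervention patient is at one hospital and every control patient at the other. The second period is what allows a treatment effect to be separated from a hospital effect.

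Sections 10.3 and 9.3 are where a reader looks for the recruitment total and the end of the study. A team working from them could recruit 50 patients per site, stop around month 6 or 7, and meet every stated total with little or no second period. The comparison would then be mainly one hospital against the other. Several outcomes are exposed to this directly, because time to scan and time in the emergency department depend on how each hospital works. If only period 1 exists, no later analysis plan can repair it.

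**Working it through.** **Reproducing the plan's figures.** Section 10.3: 2 × 50 patients + 100 clinicians = 200, which agrees. Synopsis: 6 + 6 + 1 + 3 = 16 months, which agrees. From 30 November 2019 to 24 January 2020 is 31 + 24 = 55 days, so the section 7.8 date precedes the protocol date.

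**Can the 6 months in section 10.3 mean 6 months per phase?** No. Fifty patients per site per phase would be 50 × 2 × 2 = 200 patients. The 200 in section 10.3 is 100 patients plus 100 clinicians, and the synopsis gives 100 patients in all.

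**What does the 7 months in section 9.3 cover?** It runs until outcomes have been obtained. Section 4 collects clinical outcomes within 5 days and experience within 72 hours. Seven months can therefore mean 6 months of recruitment plus follow-up (no period 2), or 7 months of recruitment (1 of the 6 months of period 2). Both are shown below.

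**Do the totals protect the crossover?** Let each site recruit x patients before the swap and 50 − x after it. Each site has x + (50 − x) = 50. Each arm takes x from one site and 50 − x from the other, again 50. Both totals hold for every x, including x = 50.

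**Share of a hospital difference that enters the unadjusted arm difference.** One hospital supplies x/50 of the intervention arm and (50 − x)/50 of the control arm, so the share is (2x − 50)/50.

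**Cost of adjusting for site and period.** The variance is (σ²/4)(1/n₁₁ + 1/n₁₂ + 1/n₂₁ + 1/n₂₂). With 25 in each cell it is σ² × 4/100 = 0.0400σ². With cells x, x, 50 − x and 50 − x, the ratio to that benchmark is 625/[x(50 − x)], and the effective N is 100 divided by the ratio.

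Assumptions: even and equal accrual at both sites, 50 per site, no cluster-period correlation.

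| Recruitment | Per site before + after the swap | Share of hospital difference | Variance ratio | Effective N |
|---|---|---|---|---|
| 6 months | 50 + 0 | 100% | not estimable | – |
| 7 months | 42.9 + 7.1 | (42.9 − 7.1)/50 = 71% | 625/306.1 = 2.04 | 49 |
| 12 months | 25 + 25 | 0% | 1.00 | 100 |

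If accrual instead ran at the 12-month rate and stopped at month 7, there would be 100 × 7/12 ≈ 58 patients (25 + 4.2 per site). The share is again 71% and the effective N is 58.3/2.04 ≈ 29.

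**The case against.** The strongest reply is that the sections that set the schedule and allocation all agree, and the stray figures are worded as forecasts. End of study is defined by an event in both 7.8 and 9.3, and nothing tells a site to skip the swap. On that view these are leftovers to tidy, in a study declared to be a feasibility study without a power calculation. This stands in part: the harm is conditional on 10.3 or 9.3 being followed. But 9.3's event is the last patient recruited, and 10.3 lets that happen within six months, so the event definitions do not secure period 2.

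Some stronger readings are tempting and are not supported:

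- A reader might infer that the November 2019 date shows period 2 being cut off. No recruitment start date is given, so the date cannot be placed within the crossover. It is obsolete and shows no more than that.
- A reader might infer that 50 per site and 50 per arm together imply 25 per site per period. They do not; 30 + 20 or 40 + 10 at both sites also meets both totals.
- A reader might take the 200 as an error. It is an open sum of patients and clinicians, and its parts stand in the same sentence.
- Section 9.2 speaks of patients needing an ambulance "for transportation to either a trauma unit or major trauma centre", which might suggest that the two sites are of different types. It does not say which hospital is which. The argument needs only that the hospitals differ on some outcome.
- A reader might conclude that 25 per cell removes all confounding. Balanced cells remove only a constant site difference and a common period effect. With two sites and one swap, treatment still coincides with the site-by-period interaction.

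**Conclusion.** The contradiction is real and is more than clerical, because it bears on the one feature that separates treatment from hospital. If section 10.3 is followed, or if month 7 in section 9.3 is follow-up only, all of any hospital difference enters the treatment difference and a hospital-adjusted effect cannot be estimated. If month 7 also recruits, about 71% enters the unadjusted difference, and adjustment roughly halves the information. The 71%, 2.04 and 49 rest on even accrual, 50 patients per site and no cluster-period correlation; the 100% follows from the design alone. None of this arises if the 6 + 6 month schedule in the synopsis and sections 5 and 7.4 is carried out in full, and the patient totals are not at fault.

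**What to change.** Bring sections 10.3, 9.3 and 7.8 into line with the synopsis and sections 5 and 7.4:

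- **10.3:** replace the 6-month study period with 12 months of recruitment, as two full 6-month periods at both hospitals. Give an expected recruitment of about 25 patients per site per period (100 patients), and show the 100 clinicians separately for clarity. Call the 25 a planning target and not a cap: a hard cap would conflict with the aim in section 7.5.1 of including nearly all eligible patients. State that reaching 50 at a site before the swap does not end recruitment there.
- **9.3:** remove the 7-month forecast, and define the end as completed follow-up of the last period-2 participant.
- **7.8:** use the same definition, and replace the obsolete date with one that follows from the actual start of recruitment.

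This is a text amendment with planned patient totals unchanged. Its cost is a later stated end date. Because the target is not a cap, actual recruitment could also exceed 50 at a site that reaches that number before the swap.
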